#### 5.3 Withdrawal Criteria

Participants are eligible to withdraw voluntarily at any time, and will be terminated from the study based on any serious adverse event, loss to follow-up, kidney transplantation, pregnancy and/or withdrawal as determined by the study investigator.

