7.2 Criteria for Removal from Treatment

7.2. 1 After six months of study drug use, the study drug will no longer be provided by Keryx free of charge. Patients may continue with Ferric Citrate as their oral phosphorus binder of choice, if desired (at their own expense).

7.2.2 Patients will discontinue treatment in the event of iron overload or any serious adverse side effect deemed attributable or possibly attributable to the study drug.

7.2.3 Patient will be removed if he/she misses the medication continuously for more than 2 weeks.

7.2.4 A patient will be removed from treatment if he/she receives a renal transplant.

7.2.5 Patient will be removed from the study if consent is withdrawn or patient is lost to follow up.

7.2.6 At the discretion of the principal investigator, a patient may be removed from study if they initiate dialysis care at an outside/Non-Kaiser Permanente facility.

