### 8.3.2 Serious Adverse Event Reporting

SERIOUS ADVERSE EVENT (SAE) is an adverse event or suspected adverse reaction if, in the view the study investigator, it meets one or more of the following criteria:

- Results in death
- Is a life-threatening adverse event (places the subject at immediate risk of death from the event as it occurred)
- Results in inpatient hospitalization or prolongation of existing hospitalization
- Results in a persistent or significant incapacity or substantial disruption of the ability to conduct normal life functions
- An important medical event that may not result in death, be lifethreatening, or require hospitalization may be considered serious when, based upon appropriate medical judgment, the event may jeopardize the patient and may require medical or surgical intervention to prevent one of the outcomes listed in this definition

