### 8.3.3 Investigator Reporting: Notifying FDA

Any SAE, including death from any cause, which occurs during the study and is deemed related or possibly related to the study drug, will be reported to the FDA and to Med Watch by the study investigator within 24 hours of detection of the SAE.

Withdrawal from the trial and all therapeutic measures taken will be at the discretion of the Principal Investigator (PI). All SAEs (related or of possible relationship to the study drug) will be followed until satisfactory resolution or until the PI deems the event to be chronic or the subject to be stable.

Any subject experiencing one or more SAEs will receive treatment and follow-up evaluations by the Investigator or will be referred to another appropriate physician for treatment and follow-up. SAEs will be monitored from the time of consent and for up to 14 days after the subject has discontinued study drug.

All adverse events, whether serious or non-serious will be followed until resolution (or stabilization, if applicable) or until the adverse event is determined by the Investigator to be no longer clinically significant.

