### 9.1.4 Withdrawal/ Final Visit (V6) ± 14 days

At end of 6 months of study drug use, or patient's withdrawal from the study, study coordinator will perform the following:

- Update comprehensive medical history
- Update limited physical exam from dialysis provider's note
- Update medical history from health records
- Collect blood specimens for aluminum level test
- Adverse event assessment
- Update laboratory values from the dialysis unit, including complete blood count, iron saturation, ferritin, phosphorus, calcium, parathyroid hormone
- Update patient's average weekly IV iron and erythropoiesis stimulating agent use.
- Perform final pill count to assess medication compliance
- Collect unused investigational product from patient who withdrew from the study
- Record patient preference for oral phosphorus binder at the end of study.

Any participant who wishes to continue with the study drug as their oral phosphorus binder of choice will be provided a prescription for Ferric Citrate. Participants who wish to return to their previous phosphorus binder will be returned to their original binder.

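### Section 5.3 makes any serious adverse event a reason to end study participation, whatever its cause, while section 8.3.3 leaves withdrawal to the PI, and nothing says which governs

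*Combined protocol and SAP*

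**What the plan says.** Four provisions bear on what happens after a serious adverse event (SAE).

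- **Section 5.3** (Withdrawal Criteria): participants "will be terminated from the study based on any serious adverse event, loss to follow-up, kidney transplantation, pregnancy". The sentence closes with "withdrawal as determined by the study investigator". It states no causality condition.
- **Section 8.3.2** defines an event as serious if, "in the view the study investigator, it meets one or more of the following criteria". One criterion is "Results in inpatient hospitalization or prolongation of existing hospitalization". Section 8.3.1 counts adverse events regardless of relation to the drug.
- **Section 7.2.2** stops treatment "in the event of iron overload or any serious adverse side effect deemed attributable or possibly attributable to the study drug". Section 7.2.3 adds: "Patient will be removed if he/she misses the medication continuously for more than 2 weeks".
- **Section 8.3.3, Investigator Reporting: Notifying FDA** (the first of two sections with that number) says: "Withdrawal from the trial and all therapeutic measures taken will be at the discretion of the Principal Investigator (PI".

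On data after exit, the Withdrawal/Final Visit (V6) in section 9.1 applies on completion or on a patient's "withdrawal from the study, study coordinator will perform the following"; it includes an update of the laboratory values. A 30-day follow-up after termination records laboratory values again. Section 10.1 compares phosphorus in the six months before and after the switch. Section 10.2 makes similar comparisons for IV iron, ESA dose, pill burden and serious events. Section 14.1 hypothesises that most patients can be moved to ferric citrate successfully. Section 14.4 (Final Analysis Plan) is marked N/A.

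**The concern.** Dialysis patients can be admitted for reasons unconnected with a phosphate binder. Section 8.3.1 itself lists heart failure, access stenosis and infection among serious events in earlier publications. Under 5.3 as worded, one such admission ends participation. Under 8.3.3 the same admission leaves the decision to the PI. Two investigators could handle identical patients differently and each cite the protocol.

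If 5.3 is followed literally, three things are at stake:

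- On-drug follow-up is cut short in the patients who are admitted, so the later on-drug months rest increasingly on patients who were not.
- Total IV iron and ESA doses (10.2) would be set against a full six-month baseline although some patients had a shorter on-drug window. The SAE comparison with the previous binder would be affected too, because a patient's participation ends at the first on-drug event.
- Exits unrelated to ferric citrate enter the transition result of 14.1, with no analysis plan to separate them.

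**Working it through.** **Step 1: the provisions side by side**

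| Provision | Trigger | Consequence | Who decides |
|---|---|---|---|
| 5.3 | Any SAE, no causality test | Leaves the study | Mandatory on the plain wording |
| 7.2.2 | Iron overload, or serious effect at least possibly due to drug | Stops treatment | Causality judgement, then mandatory |
| 7.2.3 | More than 2 weeks of continuous missed drug | Removed | Mandatory |
| 8.3.3 (Notifying FDA) | SAE | Withdrawal from the trial | PI |

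Sections 5.3 and 7.2.2 can both be obeyed: one governs leaving the study, the other stopping the drug, and 5.3 is simply wider. Sections 5.3 and 8.3.3 cannot both govern an SAE after which the PI would keep the patient in. No section ranks them.

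**Step 2: how many patients a literal 5.3 would remove**

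From the documents: N = 55 and six months on drug (section 3). The plan gives no SAE rate and no figure to reproduce, so every rate below is an assumption. With rate r per patient-year, the expected events per patient are L = 0.5r.

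- Independent events (Poisson): exits = 55 × (1 − exp(−L)).
- Clustered events (negative binomial, k = 1): exits = 55 × (1 − 1/(1 + L)).

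| r per year | L | Exits, independent | Exits, clustered |
|---|---|---|---|
| 0.25 | 0.125 | 6.5 | 6.1 |
| 0.5 | 0.25 | 12.2 | 11.0 |
| 1.0 | 0.5 | 21.6 | 18.3 |
| 1.5 | 0.75 | 29.0 | 23.6 |
| 2.0 | 1.0 | 34.8 | 27.5 |

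**Step 3: monthly phosphorus values lost**

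Planned on-drug values: 55 × 6 = 330 (V1 to V6). With m = r/12, the chance of still being in the study at month t is S(t) = exp(−mt), or 1/(1 + mt) if clustered. Each withdrawal visit is credited with one on-drug value, which favours the plan. Then lost = 55 × (6 − [S(1) + … + S(6)] − [1 − S(6)]).

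For example, at r = 1.0 the sum is 4.528 and S(6) = 0.607, so lost = 55 × (6 − 4.528 − 0.393) = 59.3.

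| r per year | Lost, independent | Lost, clustered |
|---|---|---|
| 0.5 | 31.9 (9.7%) | 29.9 (9.1%) |
| 1.0 | 59.3 (18.0%) | 53.0 (16.1%) |
| 1.5 | 83.0 (25.2%) | 71.6 (21.7%) |
| 2.0 | 103.5 (31.4%) | 86.9 (26.3%) |

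**Step 4: exits that would occur without the 5.3 trigger**

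Assume that 2 to 10% of SAEs are possibly drug-related (7.2.2, iron overload left out) and that a further 5 to 20% cause more than two weeks of missed drug (7.2.3). The combined fraction f is then 0.07 to 0.30, and exits = 55 × (1 − exp(−Lf)).

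- r = 0.5: 0.95 to 3.97 exits, against 12.2 under 5.3. The difference is 8.2 to 11.2.
- r = 2.0: 3.72 to 14.25 exits, against 34.8. The difference is 20.5 to 31.1.

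Values lost under these two rules run from 2.4 (r = 0.5, f = 0.07) to 37.7 (r = 2.0, f = 0.30), or 1 to 11% of 330. The differences still overstate what could be saved. Deaths are SAEs and end participation under any rule, and exits that the PI would judge necessary for safety are not subtracted.

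**The case against.** The strongest reply is that the protocol can be read harmoniously. Section 8.3.3 is the specific provision on SAEs and gives the PI discretion. Section 5.3 is a one-sentence general list ending in words about the investigator's determination. On that reading an SAE is a ground on which the investigator may end participation. Section 9.2, which lists hospitalisations among routine symptom checks, sits comfortably with patients staying in after an admission.

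This reading is possible, and if staff apply it most of the loss disappears. But it is not what 5.3 says. The same list includes loss to follow-up and transplantation, which 7.2.4 and 7.2.5 make mandatory grounds for removal. Where the protocol intends discretion it says so, as in 7.2.6 and in the modality-change rule of section 3. Even if discretion governs, 5.3 gives no test for using it.

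Other parts of the reply stand:

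- A reader might infer that 5.3 and 7.2.2 contradict each other. They do not, as step 1 shows.
- A reader might infer that the phosphorus result would be biased. Nothing in the documents shows that admitted patients respond differently to the switch. Each patient is his or her own control, and no text excludes the values of those who leave early.
- Section 14.1 does not say that a withdrawal counts as a failed transition.
- The withdrawal visit recovers some data. The 30-day values add laboratory results, but after the study drug period.
- The counts mainly reflect the assumed rates.

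**Conclusion.** The concern holds in a limited form. Section 5.3 as written ends participation for any SAE, section 8.3.3 leaves that decision to the PI, and the protocol does not say which prevails. Followed literally, 5.3 shortens on-drug follow-up selectively in patients who are admitted and adds exits unrelated to the drug.

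The size depends on assumed rates. At 0.25 to 2.0 SAEs per patient-year, about 6 to 35 of 55 patients would leave within six months. At 0.5 to 2.0 per year, about 9 to 31% of the planned monthly on-drug phosphorus values would be lost across the two event models. These are upper bounds on the avoidable loss, because some exits occur under any rule, and the loss is far smaller if 5.3 is applied with discretion.

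The direction and size of any effect on phosphorus are unknown. Nor is this a loss of power: the protocol summary says the study is not powered for significance. The issue is who remains under observation on drug. The correction is cheap and worth making, but it is not a fatal flaw.

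**What to change.** In section 5.3, replace the unqualified SAE trigger with: *a serious adverse event judged at least possibly related to study drug, or after which the PI judges continuation unsafe*. Add that an unrelated SAE does not by itself end participation. Cross-reference this rule in 7.2.2 and in 8.3.3 (Notifying FDA), so that the three sections give one answer. Leave the iron-overload trigger in 7.2.2 and the two-week rule in 7.2.3 unchanged.

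The safety exits are kept. The cost is one wording change, two cross-references and a protocol amendment, subject to sponsor and IRB approval. No visits, tests or patients are added.

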### **6** STRATIFICATION/ RANDOMIZATION SCHEME

No stratification or randomization scheme is needed in this single arm study.

### 7 STUDY PRODUCT ADMINISTRATION AND TOXICITY MANAGEMENT PLAN

### 7.1 Administration

Ferric Citrate will be administered orally with water within 30 minutes of a meal. Study drug dosing conversion will be based on type of phosphate binder that the patient is taking at the initiation of the study. Given the binding capacity of the different binders (appendix table), we will make the conversion as below

- i. For calcium carbonate, calcium acetate, sevelamer carbonate
  - 1. 1 tablet with meals will convert to 1 tablet of ferric citrate with meals
  - 2 tablets or higher will convert to 2 tablets of ferric citrate with meals and will be titrated up based on week 2, week 4, and subsequent routine monthly labs
- ii. For Lanthanum
  - 1 or more tablets with meals will convert to 2 tablets will convert to 2 tablets of ferric citrate with meals and will be titrated up based on week 2, week 4, and subsequent routine monthly labs

All subsequent phosphate binder dose adjustments will be based on decisions made by the nephrologists based on routine clinical laboratory results and patients subjective tolerability to binders. Laboratory monitoring of baseline labs (Calcium, phosphorus, iron levels, ferritin, hemoglobin, hematocrit) will be every 2 weeks for the first 2 months, and ferric citrate dose may be titrated every 2 weeks until stable phosphorus control is obtained.

7.1b Management of IV iron during study phase

If patient is receiving IV iron at the time active study starts (ie, start of ferric citrate administration), IV iron will be discontinued if the patient's ferritin level is > 200 ng/ml and iron saturation is > 20%. Otherwise IV iron may be continued until patient's serum ferritin level is > 200 ng/ml and iron

Page 18 of 35

saturation is > 20% with concomitant use of the study drug. IV iron will not be used if the iron saturation is greater than 50%, even if a patient's serum ferritin level falls below 200 ng/ml.

If during the active study period a patient's serum ferritin level falls below 200 ng/ml and/or iron saturation level falls below 20%, IV iron may be restarted, at the discretion of the study investigator(s).

7.2 Criteria for Removal from Treatment

7.2. 1 After six months of study drug use, the study drug will no longer be provided by Keryx free of charge. Patients may continue with Ferric Citrate as their oral phosphorus binder of choice, if desired (at their own expense).

7.2.2 Patients will discontinue treatment in the event of iron overload or any serious adverse side effect deemed attributable or possibly attributable to the study drug.

7.2.3 Patient will be removed if he/she misses the medication continuously for more than 2 weeks.

7.2.4 A patient will be removed from treatment if he/she receives a renal transplant.

7.2.5 Patient will be removed from the study if consent is withdrawn or patient is lost to follow up.

7.2.6 At the discretion of the principal investigator, a patient may be removed from study if they initiate dialysis care at an outside/Non-Kaiser Permanente facility.

7.3 Comorbidities

Participants' comorbid conditions will be managed by their physicians per usual protocol.

### 8 ASSESSMENT OF EFFICACY AND SAFETY

### 8.1 Toxicity Monitoring

Laboratory monitoring will occur on a bi-monthly basis for the first two months, then on a monthly basis and as needed. Laboratories monitored will include

Page 19 of 35

calcium, phosphorus, iron levels, ferritin, and complete blood count. In addition, participants will be screened by the study coordinator either in person or via the phone every week to two weeks on adverse side effect monitoring.

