### **1 INTRODUCTION**

### 1.1 Background

High serum phosphorus levels are associated with a greater risk of mortality among patients with chronic kidney disease (CKD) and non-chronic kidney disease populations(1-5). Elevated phosphorus levels are also associated with increased cardiovascular complications among dialysis patients. As renal function declines, dietary intake and adherence to phosphate binders becomes more and more important for phosphorus control and prevention of CKD-associated mineral bone disease (CKD-MB).

Reduction of serum phosphorus levels by phosphate binding agents is associated with a lower risk of both cardiovascular and all-cause mortality in patients with end stage renal disease (ESRD)(6), but side effects of phosphate binders, high pill burden, and long term safety concerns remain an issue. Calcium based binders are associated with vascular calcifications(7, 8), which led to national guidelines that limit total elemental calcium intake in ESRD patients. Aluminum hydroxide and lanthanum carbonate are potential alternatives to calcium based binders and sevelamer carbonate/hydrochloride, but pose the risk for long term buildup in the body and potential untoward consequences since they are metals. (9, 10)

While much effort is placed on dietary counseling regarding low phosphorus diets, proper use of phosphate binders and vitamin D analogs, a high prevalence of CKD-MB associated complications still exists among patients, especially dialysis dependent patients. Valvular heart disease, isolated systolic hypertension, calcific uremic ateriolopathy (calciphylaxis), peripheral vascular disease, and hip fractures are all more common in CKD patients, leading to greater morbidity and mortality(11, 12). The pathophysiology of vascular disease in CKD patients is complex. It occurs as a consequence of reduced renal function, increases in calcium and phosphorus balance, precipitation of calcium and phosphorus and the uremic milieu. Previous observations using electron beam computed tomography have demonstrated an association between higher calcification and cardiovascular disease.(12, 13)

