### **3 STUDY DESIGN**

- Type: non-randomized, single arm, phase IV, cohort pilot study
- Study population: end stage renal disease patients who are on chronic hemodialysis or peritoneal dialysis with elevated serum phosphorus.
- 55 chronic dialysis patients (28 hemodialysis and 27 peritoneal dialysis) who are currently using oral phosphorus binders will be enrolled. Potential participants will be screened from both the chronic hemodialysis unit and the home dialysis unit at the LAMC site. Potential study patients will be approached by study investigators during any routine visit. If the patient consents to participation, the study coordinator will see patients during the same visit. If study staff is unable to meet with patient during routine visit or if the patient requests more time to consider participation, peritoneal dialysis patients may be asked to return to clinic for an additional visit to sign the informed consent. This will only apply to peritoneal dialysis patients. If the patient chooses not to enter the study, the reason will be noted by the study coordinator. At the appropriate time in the study, the study coordinator will dispense the study medication, Ferric Citrate, and provide instructions per study protocol. The study coordinator will meet with the participant every month during either a hemodialysis visit (for hemodialysis patients) or a monthly clinic visit (for peritoneal dialysis patients) with his/her provider, and laboratory values/data and study questionnaire will be updated each month. If at any time during the study, a peritoneal, dialysis patient changes to hemodialysis, the patient can continue study at the principal investigator's discretion. If at any time during the study, a hemodialysis patient changes dialysis to peritoneal, the patient can continue on study at the principal investigator's discretion. In such event, patient's group assignment for analysis will be determined at the discretion of the Principal Investigator. Patients will be allowed to continue in the trial given that they can continue to meet all study participation requirements. The six month period prior to enrollment will be used to evaluate the

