### **4 STUDY PRODUCT INFORMATION**

4.1 Description

Ferric Citrate is known chemically as iron (+3), x (1, 2, 3-propanetricarboxylic acid, 2- hydroxy-), y (H2O) x=0.70 - 0.87, y = 1.9 - 3.3.

Ferric citrate's trade name is Auryxia. Auryxia 210 mg ferric iron tablets, equivalent to 1g ferric citrate, are film-coated, peach-colored, and oval-shaped tablets embossed with "KX52". The inactive ingredients are pregelatinized starch and calcium stearate. In addition, the film-coating contains the following inactive ingredients; hypromellose, titanium dioxide, triacetin, and FD&C Yellow #6/Sunset Yellow FCF Aluminum Lake, FD&C Red #40/Allura Red AC Aluminum Lake, and FD&C Blue #2/Indigo Carmine Aluminum Lake.

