### **9 STUDY SCHEDULE: CLINICAL/ LABORATORY EVALUATIONS**

9.1 Study Schedule

### 9.1.1 Screening Visit

Screening visit will occur during the participant's routine monthly dialysis follow up visit by the participant's nephrologist. Patients who meet the inclusion criteria based on chart review by the study coordinator will be approached and

offered to discuss the study in an opt-in fashion introduced by the patient's nephrologist.

Obtain and document consent from potential patient

- Review medical history to determine preliminary eligibility based on protocol eligibility criteria
- Obtain comprehensive medical history and limited physical exam from the medical history, supplemented by information from the patient
- Assign participant a study ID
- Collect blood specimens for aluminum level

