#### 9.2 Clinical Evaluations

**Laboratory testing will include**: complete blood count, iron saturation, ferritin, phosphorus, calcium, parathyroid hormone, and aluminum level

**Symptoms evaluation will include**: any hospitalizations, infections, GI bleed, dialysis access complications, diarrhea, constipation, abdominal discomfort, abdominal distension, duodenal ulcer, nausea, and stool color changes.

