9.3 Laboratory Evaluations

Routine dialysis laboratory values will be collected from the patient's dialysis unit on a monthly basis per current standard of care. At week 2 and week 6, additional complete blood count, iron saturation, and ferritin levels will be collected at the patient's dialysis unit. Six aluminum levels will be drawn for each participant over the course of the study. Aluminum level tests will be collected in a single vial (royal blue top tube, approximately 4 ml of blood) by the study coordinator and transported on ice to the LAMC laboratory.

9.4	Study Calendar
-----	----------------

Study Procedures	Screening	Baseline Data to be collected	Study phase monthly Visit # 1-5, V1-V5 	Laboratory on week 2 and week 6 	weekly in-center & bi-monthly home dialysis follow up	End of Treatment	30 post follow up
Signed Consent Form	X 4						
Assessment of Eligibility	Х	Х					
Comprehensive History	Х					Х	
Limited Physical Exam	Х		Х			Х	
Update Medical History		Х	Х			Х	
Complete Blood Count	Х	Х	Х	Х		Х	
Iron saturation	Х	Х	Х	Х		Х	
Ferritin	Х	Х	Х	Х		Х	
Phosphorus	Х	Х	Х	Х		Х	
Calcium	Х	Х	Х	Х		Х	
IV iron use	Х	Х	Х			Х	
Parathyroid Hormone (iPTH)	X	Х	Х			Х	
Aluminum level 			Х				
Mean weekly ESA agent dose	Х	Х	Х			Х	
Medication dispensed			Х				
Medication compliance update			X		X	X	
Adverse Event Assessment		X	Х		Х	Х	Х

- 1 Each visit will correspond with monthly hemodialysis or peritoneal dialysis monthly laboratory result round
- 2 Blood test will be drawn during routine hemodialysis. Home dialysis patients will be asked to go to any KPSC laboratory (normal routine for these patients).
- 3 Aluminum level blood tube will be brought by study coordinator to be drawn at hemodialysis with the patient's regular monthly labs. Aluminum test tube will be transported on ice to the LAMC laboratory. Home dialysis patients will be referred to any KPSC laboratory for aluminum testing, when needed.
- 4 Screening visit: If study staff is unable to meet with patient during routine visit or if the patient requests more time to consider participation, peritoneal dialysis patients may be asked to return to clinic for an additional visit to sign the informed consent. This will only apply to peritoneal dialysis patients.

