### **13 STUDY OVERSIGHT**

### 13.1 Data Safety Review Panel

In this pilot study with an FDA approved medication, a modified Data Safety Review Panel will be established with 2 study investigators and one non-study nephrologist. The Data Safety Review Panel will meet on a quarterly basis to evaluate any adverse events, including patients whose serum ferritin increased to >1500. If Data Safety Review Panel identifies new drug related adverse event, reporting will follow per previously outlined protocol. Study coordinator will help to keep records of the Data Safety Review Panel meetings.

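### Aluminum is drawn specifically for the study and sits in the primary endpoint, but no safety section routes an individual rise to review, and its draw schedule conflicts

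*Combined protocol and SAP*

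**What the plan says.** Aluminum appears in the testing and endpoint sections:

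- 9.1.1 (Screening Visit) orders a sample: "Collect blood specimens for aluminum level". Section 9.1.3 orders one monthly at V1-V5, in a tube the coordinator provides, and the Withdrawal/Final Visit section (V6) orders one more.
- 9.2 lists the study tests as "complete blood count, iron saturation, ferritin, phosphorus, calcium, parathyroid hormone, and aluminum level".
- 9.3 states the count: "Six aluminum levels will be drawn for each participant over the course of the study".
- 10.1 includes aluminum levels in the primary before/after endpoint.

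It is absent from the safety sections:

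- 8.1 lists "calcium, phosphorus, iron levels, ferritin, and complete blood count".
- 8.2 sets rules for iron saturation and ferritin only.
- 13.1 has the panel meet quarterly to "evaluate any adverse events, including patients whose serum ferritin increased to >1500".

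Two background statements bear on how the gap is read. Section 1.1 says of aluminum hydroxide and lanthanum carbonate binders that they "pose the risk for long term buildup in the body". Section 4.1 lists aluminum lake colorants among the inactive film-coat ingredients, for example "FD&C Yellow #6/Sunset Yellow FCF Aluminum Lake", without a quantity. Section 14.4 (Final Analysis Plan) is marked not applicable.

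**The concern.** A blood test added for the study and repeated through treatment would normally have a stated reader and a stated use. Here the only stated use is as a before/after level in 10.1. If a few patients rise and the rest do not, a group level is a poor way to notice it, and it cannot say how many rose. No provision obliges anyone to bring such a patient to the safety panel while treatment continues.

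The before/after comparison also needs a value from before the drug. Depending on which part of section 9 is followed, a participant may not have one.

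**Working it through.** **1. The stated number of draws.** Section 9.3 says six per participant. Counting from the other sections:

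| Source | Draws | Total for 55 |
|---|---|---|
| 9.4 calendar (marks V1-V5 only) | 5 | 5 × 55 = 275 |
| 9.3 text | 6 | 6 × 55 = 330 |
| Visit text: screening 1 + V1-V5 5 + V6 1 | 7 | 7 × 55 = 385 |

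Six is reached only by leaving out one draw that the visit text orders: either screening (V1-V5 + V6 = 6) or V6 (screening + V1-V5 = 6). The cohort size comes from section 3: "55 chronic dialysis patients (28 hemodialysis and 27 peritoneal dialysis". The totals assume that home dialysis patients follow the same schedule. Calendar footnote 3 refers those patients for aluminum testing only as the need arises. That could mean whenever a draw falls due or only on indication, and it affects 27 of the 55.

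**2. The pre-drug value.** Study drug is first dispensed after the baseline data are recorded (9.1.2), so V1 is already on drug. The six months of retrospective laboratory data in 9.1.2 do not include aluminum. The single screening draw in 9.1.1 is therefore the only pre-drug source, and the calendar does not mark it. A site working from the calendar would have no before value for this part of the primary endpoint.

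**3. Where an individual result can go.**
- Section 3 has laboratory values assessed and logged monthly during treatment. It names no reviewer for aluminum and no next step.
- The explicit coordinator-investigator laboratory review, at weeks 2 and 6, covers a panel without aluminum.
- 8.2 and 7.2.2 name iron saturation, ferritin, iron overload and attributable serious side effects.
- 13.1 covers adverse events and names high ferritin. The adverse event definition in 8.3.1 does not say whether a symptomless laboratory rise counts.
- The 30-day follow-up laboratories omit aluminum, so a high V6 value has no planned repeat.

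**4. What a group mean would show.** Assume, for illustration, equal baselines and no change in the other patients. If m of N = 55 patients double, the mean rises by m/N:

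- m = 1: 1/55 = 1.8%
- m = 3: 3/55 = 5.5%
- m = 5: 5/55 = 9.1%

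**5. Could one or more of 55 be affected?** The documents give no rate, so a range is assumed. The chance of at least one affected patient is 1 − (1 − p)^55: 42% for p = 1%, 67% for 2%, 94% for 5% and 99.7% for 10%. These figures show only that, if marked rises occur at rates of this order, a cohort of this size could well contain one. They are not evidence that such rises occur.

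**The case against.** The case on the other side is substantial, and part of it stands.

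- **Values are looked at monthly.** A reader might infer that a rise would go unseen until the final analysis. Section 3 does not support that, because laboratory values are to be assessed and logged every month. What is missing is a designated route from that look to safety review.
- **The tablet is not shown to carry an accumulation risk.** A reader might join the buildup warning in 1.1 to the colorants in 4.1. The warning concerns aluminum and lanthanum used as binders, and 4.1 lists film-coat ingredients without amounts. The documents never say why aluminum is drawn. The Protocol Summary admits users of aluminum binders (5.1.1 does not list them), so the draws could equally track change after leaving such a binder.
- **The lists in 8.1 and 9.2 need not match.** The wording of 8.1 is not exclusive, and parathyroid hormone is likewise in 9.2 but not in 8.1. So this is an omission, not a contradiction. The parallel is incomplete, though: parathyroid hormone is among the routine monthly dialysis laboratories, while aluminum needs a separate study tube.
- **General provisions exist.** Investigators may change the dose or withdraw a patient, and the panel sees any adverse event, with ferritin as an example rather than a limit. These provisions permit a response to an aluminum rise but do not require that anyone bring it forward.
- **The percentages are illustrative.** Doubling and equal baselines are assumptions, and 10.1 does not clearly prescribe a mean for aluminum. With no analysis plan, however, no patient-level summary is specified either.

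**Conclusion.** The point holds in a limited form. Aluminum is a study-specific, repeated test within the primary endpoint, yet 8.1, 8.2 and the one laboratory criterion named in 13.1 leave it out. No section sends an individual symptomless rise to safety review. On the illustrative assumptions, a group mean would move 1.8% for one doubling and 9.1% for five, so the endpoint in 10.1 would show little of a rise confined to a few patients. If former aluminum-binder users enroll, baselines would differ, and falls in those patients could further offset rises in others.

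Separately, and without any assumption about risk, the draw schedule conflicts (5, 6 or 7 per participant), testing of the 27 peritoneal dialysis patients is unclear, and the only pre-drug value is missing from the calendar.

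The documents do not support saying that the tablet causes aluminum to accumulate, that results stay unread until the end, or that exactly 330 results will exist.

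**What to change.** 1. Reconcile 9.1.1, 9.1.3, the Withdrawal/Final Visit section (V6), 9.3 and the 9.4 calendar with its footnote 3. Every participant, hemodialysis and peritoneal, should have the screening (pre-drug) aluminum value and the same on-drug draws. This comes first, because the next steps depend on it.
2. Add aluminum to the laboratories in 8.1.
3. Give the existing 13.1 panel, at each quarterly meeting, a per-patient listing of aluminum change from the pre-drug value.
4. In 10.1, report beside the group level the number of patients who rise above the testing laboratory's reference limit, with the number who had a pre-drug value as the denominator.

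Any action level is for the investigators and the panel to set; none is proposed here.

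The cost is wording changes, one listing per panel meeting (about three if meetings run through a nine-month study, 9/3 = 3) and one extra summary line. If all draws in the visit text are kept, no sample is added to what that text already orders. A site that had planned from the calendar would need up to two more tubes per participant, at most 2 × 55 = 110.
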